**(1) ABSTRACT:**

Significant morbidity, mortality, and related costs are caused by traumatic brain injury (TBI). A simple, effective, and lightweight device worn by athletes or war fighters in the field, designed to mitigate TBI resulting from blast trauma or concussive events, would save lives, and the huge costs incurred for life-treatment of surviving victims. An externally-worn medical device (the Device) that applies mild jugular vein compression according to the principle of the Queckenstedt Maneuver, is being developed by Q30 Sports Science, LLC (Q30). Preliminary research suggests that the Device has the potential to reduce the likelihood of TBI. The currently developed collar (Smith 2009, Smith and Fisher 2011, Smith and Fisher 2011, Smith 2012) has been approved for studies in humans (IRB 2013-2240) and the results indicate safety for use during high demand and maximal exertion activities. Regarding safety, the externally worn collar is meticulously designed to mimic the body's own omohyoid muscle actions upon the jugular veins that will provide similar pressure and volume increases not to surpass that of a yawn or the mere act of just lying down.

This study will investigate the effectiveness of this device in high school athletes playing a non-helmeted sport such as soccer. Athletes participating in this study will be randomly assigned to one of two groups: 1) Device wearing during the season or 2) Non-device wearing during the season. This study will focus on the use and effectiveness of the device solely in females, as male football and hockey players have previously been investigated. All participants will be outfitted with an adhesive patch-like accelerometer (which will be placed behind the ear (*Xpatch-X2 Biosystems* [http://www.x2biosystems.com/x2\\_x\\_patch/](http://www.x2biosystems.com/x2_x_patch/)) which will measure the magnitude of every impact to the head sustained by the athlete. Effectiveness of the device will be determined via differences in longitudinal brain imaging and functional testing following competitive soccer participation. A subset of athletes who report a diagnosed concussion will also receive additional brain neuroanatomical and neurophysiological testing within a week following the diagnosed concussive event. At each of these time points participants will also undergo various neurocognitive assessments outlined below.

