**(6) SELECTION & RECRUITMENT OF PARTICIPANTS:**

We will recruit up to 150 study participants. The participants (age 14-19 years old) will be recruited from a local school district and local sports clubs and teams. Participants will be recruited using a top-down approach. We have gained the consent and the cooperation of the school district administrations. Presentations and letters from the research team will be given to each participating school to detail the participation requirements and study risks.. Questions regarding participation will be answered during the presentations or through e-mail or phone. Participants will be contacted via telephone to further explain the study, answer any additional questions and to enroll them in the study. The participants and parents/guardians who voluntarily agree to participate will be scheduled to complete the pre-participation testing. The participant and parent/guardian will read and sign the “Consent to Participate in a Research Study” form, approved by the Institutional Review Board of Cincinnati Children’s Hospital. If the participant and parent/guardian does not read or sign the form, they will not participate in the study. Once the potential study participants/school teams are identified, they will be allocated to one of two groups: 1) Device wearing during the season or 2) Non-device wearing during the season. This research does not mandate that the participant maintains participation in their sport. The desire to participate in the sporting event is an independent, personal decision separate from the decision to enter into this study. If any athlete chooses to stop participation in the sporting activity then they will also be withdrawn from the study, due to no longer meeting inclusion criteria.

Inclusionary criteria include:

- Female

- Normal healthy volunteer
- Able to provide written consent
- Must be 14 years or older and a participant on a high school soccer team

Exclusionary criteria include:

- Unable to provide written consent
- History of neurological deficits, previous cerebral infarction, or severe head trauma as indicated through pre-season screening:
- Medical contraindications to restriction of venous outflow via the internal jugular veins (known increased intracerebral pressure, metabolic acidosis or alkalosis)
- Glaucoma (Narrow Angle or Normal Tension)
- Hydrocephalus
- Recent penetrating brain trauma (within 6 months)
- Known carotid hypersensitivity

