#### **(8) STUDY PROCEDURES:**

##### **Location I – Brain Imaging-Performed at CCHMC Imaging Research Center**

### **MR imaging data Acquisition**

Magnetic Resonance Imaging (MRI), including sequences outlined in Table 1 are all based on the concept of using magnetic fields and radio waves to make chemical, anatomical and physiological assessments with in the living tissue. This technology has been utilized for diagnostic and research purposes since the early 1980s.

This testing will consist of a minimum of 2 MRI sessions (preseason, and post season) and additional scans following any clinically diagnosed concussions, all inside a 3T scanner at the CCHMC Imaging Research Center. During the acquisition of MR images, the study participants will lie on the scanner table. For most portions of MR acquisition, the study participants will only be instructed to lie still. For other parts of the acquisition, study participants will be asked to answer questions that will assess their cognitive ability and working memory. Participants will be allowed to communicate with the MR operator via an always-on, two-way intercom at any time. In addition, the participants have a hand-held air ball to squeeze in the event that they elect to be removed from the magnet immediately. The study participants have control over their presence in the magnet, which in turn tends to minimize feelings of claustrophobia. As magnetic resonance imaging employs the use of strong magnets, patients will receive a standard preoperative screening questionnaire regarding the potential for ferromagnetic objects within their bodies to ensure their safety during the study. Participants will be screened for MRI specific contraindications such as:

- Braces or permanent metal dental work
- Insulin pump
- Cardiac pacemaker
- Cochlear implants
- Hearing aids
- Aneurysm clips
- Orthopedic pins, wires, screws, or plates
- Any other exclusionary criteria as documented on the MRI safety screening poster included with recruitment materials

Those participants with any aforementioned contraindication may be excluded from the imaging portion of the study but will still be eligible to participate in the rest of the study procedures.

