#### *Simple Reaction Time*

A repeated measures mixed-model design will be employed. A total of up to three groups (Device vs. no device vs concussion) will be examined using a 3 x 2 (group by time point; pre-season vs. post-season) ANOVA.

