**Adverse Events.** During the course of the investigation, injuries consistent with the sports being monitored are expected to occur (E.g. concussion, musculoskeletal injury, bone fractures). Care of all injuries will follow standard of care as directed by the team's athletic trainer and/or the participants treating physician. CCHMC will not be responsible for the medical treatment of any injuries that are not directly related to wear of the Q-collar device. In the case of an adverse event that is determined to be directly related to the wear of the Q-collar during competitive play, the principal investigator will report such event to Cincinnati Children's Hospital Medical Center IRB as any future funding organizations in a manner consistent with the requirements of each organization. As described in the consent, if a participant believes they have sustained an injury as a result of the study then they are instructed to contact the principal investigator or director of social services who in turn will then contact CCHMC IRB and necessary funding institutions, as aforementioned. If a participant sustains an injury during testing they will be referred to the most appropriate medical facility or seek medical attention by the physician/medical specialist of their choice.

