### **(13) RISK/BENEFIT ANALYSIS:**

Participants will be approached for participation via the appropriate method. The purpose and the study protocol will be fully explained in conversation and with the informed consent process.

On the day of the study, the investigators will confirm that the volunteer participant has no health impairment as outlined in the exclusion criteria. Time will be taken to repeat the aims of the study, test protocol, and to answer any remaining questions posed by the participant.

The methods described in this protocol have been used extensively in previous testing in the laboratory. During previous testing, there have been no reported injuries, adverse events or complications. Additionally, the investigators have considered potential risk for injury and have taken additional steps, described in the protocol, to minimize these risks.

Subject participation will be halted should an adverse event while wearing the collar, such as syncope, occur. Any adverse events will be immediately reported. The safety officer will evaluate all adverse events and will determine if early stopping of the study due to safety concerns is warranted. Given the study design and sample, we do not deem futility or efficacy stopping rules are warranted.

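### The individual halting rule ends participation rather than collar wear, can be triggered only in the collar arm, and, read literally, conflicts with the planned post-concussion follow-up

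*Combined protocol and SAP*

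**What the plan says.** Section 13 (Risk/Benefit Analysis) sets the rule for the individual athlete: "Subject participation will be halted should an adverse event while wearing the collar, such as syncope, occur". Syncope is the only example given. The rule names no severity and no link to the device, and it does not say whether what ends is collar wear, the athlete's season in the study, or her post-season testing.

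Section 12, under the label Adverse Events, says that "injuries consistent with the sports being monitored are expected to occur (E.g. concussion, musculoskeletal injury, bone fractures" and leaves their care to the usual providers. The same paragraph treats device-related events as a separate class for IRB reporting: "In the case of an adverse event that is determined to be directly related to the wear of the Q-collar during competitive play".

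Section 6 has a second removal rule, which applies to both arms: "If any athlete chooses to stop participation in the sporting activity then they will also be withdrawn from the study".

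Other parts of the protocol expect concussed athletes to stay in the study:

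- Abstract: "A subset of athletes who report a diagnosed concussion will also receive additional brain neuroanatomical and neurophysiological testing".
- Section 8, MR imaging: "additional scans following any clinically diagnosed concussions".
- Section 9, Simple Reaction Time: "A total of up to three groups (Device vs. no device vs concussion) will be examined", at pre-season and post-season.
- Section 17: payment for each completed session after a new concussion.

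None of these four is limited to one arm.

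**The concern.** The comparator wears no device and no sham, so an event that occurs while wearing the collar is possible in one arm only. If a collar athlete and a control athlete suffer the same injury in play, the section 13 wording reaches the first and not the second. The trial judges the device on pre- to post-season change by arm (sections 2 and 9). An athlete whose participation ends before the post-season visit contributes no change score, and section 13 can create that gap only on the collar side.

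The gap would have to be handled in the analysis, but the plan gives no analysis set and no missing-data rule for this trial. Intention-to-treat is mentioned only for the earlier football study in section 3. Post-season data that were never collected cannot be recovered later.

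**Working it through.** The plan gives no figure on this point, so there is none to reproduce. The check has two parts.

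**1. The passages side by side**

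- *Broad reading of section 13 (any adverse event while collared).* With the injuries listed in section 12, a collar athlete concussed in play is halted. The abstract, section 8, section 9 and section 17 then plan testing, scans, a pre/post-season analysis group and payment for an athlete whose participation has ended. Both cannot be followed.
- *Narrow reading (syncope-type events only).* The conflict over concussion disappears. The rule still ends participation, it still acts in one arm only, and nothing in the documents reviewed keeps the athlete for her post-season visit. Those lost would be collar athletes who had an event of that kind while wearing the device.
- *Section 6.* This is a separate route: it depends on the athlete's own choice to stop playing and is open to both arms. Section 13 adds a study-imposed, event-triggered route in one arm.

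**2. Scale**

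Inputs from the documents: up to 150 athletes (section 6); concussion rates of 4.5 per 10,000 and 0.36 per 1,000 exposures (section 3); two-sided 5% tests (section 9). Assumptions: equal allocation, so 75 per arm; 40 to 80 exposures per athlete; independent athletes; every halted athlete lacks post-season data.

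Expected collar-arm concussions = 75 × exposures × rate:

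- low: 75 × 40 × 0.00036 = 1.1
- high: 75 × 80 × 0.00045 = 2.7

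That is 1.4% to 3.6% of 75.

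For other injuries the documents give no rate. At an assumed 2 to 5 per 1,000 exposures, athletes with at least one injury = 75 × (1 − exp(−rate × exposures)), which gives 5.8 to 24.7 of 75.

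Suppose a share f of the collar arm is lost, and those lost would have changed D SD more, in the harmful direction, than those who remain. With no true effect:

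- bias (collar minus control) = −f × D
- SE = √[1/(75(1 − f)) + 1/75]
- rejection rate = Φ(−1.96 + |bias|/SE) + Φ(−1.96 − |bias|/SE)

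| f | D | bias (SD) | rejection rate |
|---|---|---|---|
| 0.036 (concussion only, upper end) | +1.0 | −0.036 | 0.0555 |
| 0.036 | +0.5 | −0.018 | 0.051 |
| 0.10 (assumed) | +0.5 | −0.05 | 0.060 |
| 0.30 (assumed) | +0.5 | −0.15 | 0.133 |
| 0.30 (assumed) | +1.0 | −0.30 | 0.385 |
| 0.10 (assumed) | −0.5 | +0.05 | 0.060 |
| 0.30 (assumed) | −0.5 | +0.15 | 0.133 |

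Negative bias makes the collar look better; positive bias makes it look worse. For comparison, 75 per arm detects (1.96 + 0.84) × √(2/75) = 0.46 SD with 80% power. The concussion-only shift of at most 0.036 SD (at D = 1) is under a tenth of that.

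**The case against.** The strongest reply is that the broad reading was not meant. Syncope is a device-type event. Section 13, just before the rule, names injuries and adverse events as separate items. Section 12 sets device-related events apart, and the concussion follow-up makes sense only if concussed athletes remain. This has force: the text is better described as ambiguous than as a settled plan to remove injured collar athletes. It does not dispose of the point. Staff must apply the words as written, section 12 shows that a relatedness condition could be stated, and the missing retention provision survives the narrow reading.

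A reader might infer that only collar athletes are removed after injury. The documents do not support that. A control athlete who chooses to stop playing after an injury is withdrawn under section 6.

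A reader might also infer that the collar is favoured. That needs D to be positive, which is plausible for concussed athletes but not established. Section 3 reports initial evidence from the football study that change in axial diffusivity in some regions correlated with impact exposure in the no-collar group. An athlete sidelined by a sprain or fracture takes fewer impacts and might change less, and losing her would count against the collar. Some outcomes are also less exposed. For reaction time and oculomotor measures concussed athletes form their own group, so losing some of them thins that group without shifting device against no device. In the Poisson analysis the first concussion still counts and the offset shortens.

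Two further limits stand. Consent pages were not available for review, so silence on retention is established only for the text seen. Section 8 describes supplying the intervention by team, so the independence assumed in the standard error may not hold.

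**Conclusion.** The point holds as a defect of wording with a consequence for data collection. Section 13 ends participation without requiring device-relatedness and without separating collar wear from study follow-up. Only the collar arm can trigger it, and read literally it conflicts with the post-concussion plan in the abstract and sections 8, 9 and 17. The risk is differential loss of post-season data in the collar arm, in an uncertain direction.

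If the loss is confined to concussion, it is about 1 to 3 athletes and the test stays close to its nominal 5%, given 75 per arm and 40 to 80 exposures each. A material bias arises only if many other injuries trigger a halt. The 10% to 30% rows are illustrations without a source in the documents, and their sign follows from the assumed sign of D. They should not be cited as an estimate of the false-positive rate. The case for changing the text is that the loss is one-sided, avoidable and irreversible once the season ends.

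**What to change.** Reconcile sections 12 and 13 with the abstract and sections 8, 9 and 17 on which events trigger a halt. The clinical criterion is for the investigator and safety officer to set.

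Whatever the trigger, reword section 13 so that stopping collar wear and leaving the study are two different things. State that an athlete whose collar wear is stopped stays in her assigned arm for analysis and attends the planned post-season assessments, and the post-concussion assessments if she is concussed, unless she withdraws consent.

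The cost is protocol wording, and consent wording if the consent form repeats the rule. The visits are already part of the plan. The downside is that the collar arm will include some athletes with shorter wear. The change does not touch section 6, which will still withdraw athletes in either arm who choose to stop playing.

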**(14) DATA SAFETY & MONITORING:**

The Safety Officer ([name], MD) who has extensive experience in the management of concussion at the professional, collegiate, high school and middle school level will act in an advisory capacity to the Principal Investigator (PI) to monitor patient safety and progress for the clinical trial, “Concussion Prevention Device”. [name] will be the contact person for severe adverse event reporting.

The Safety Officer’s responsibilities are to:

- review the research protocol, informed consent documents and plans for data safety and monitoring;
- evaluate the progress of the trial, including periodic assessments of data quality and timeliness, participant recruitment, accrual and retention, participant risk versus benefit, performance of the trial site, and other factors that can affect study outcome;
- consider factors external to the study when relevant information becomes available, such as scientific or therapeutic developments that may have an impact on the safety of the participants or the ethics of the trial;
- review study performance, make recommendations and assist in the resolution of problems reported by the PI;
- protect the safety of the study participants;
- report to the PI on the safety and progress of the trial;
- make recommendations to the PI concerning continuation, termination or other modifications of the trial based on the observed beneficial or adverse effects of the treatment under study;
- ensure the confidentiality of the trial data and the results of monitoring; and, assist the PI by commenting on any problems with study conduct, enrollment, sample size and/or data collection.

The Safety Officer and PI will hold meetings to review the data safety, the first of which will be held prior to initiation of the trial to discuss the protocol, approve the commencement of the trial, and approve the plans for monitoring the study. Meetings with the safety officer will be determined by the PI and will be closed to the public because of confidentiality considerations. An emergency meeting may be called at any time by the Safety Officer, or by the PI, should questions of participant safety arise.

[name], Division of Sports Medicine, will serve as a study monitor for this project, while the PI and study coordinators will be responsible for monitoring data quality and adverse events. The monitor will review adverse events and unanticipated events at the time they occur and will report his assessment of the event(s) to the PI.

This research study involves only minimal risk for participants (see Risk/Benefit Analysis section (15)). Further assurances regarding participant safety and protection of private and confidential participant information have been outlined in the Potential Risks, Discomforts, Inconveniences and Precautions section (14), the Privacy section (18) and the Confidentiality section (19). If during the, preliminary analyses the research team identifies strong evidence of harm from the Q-collar device the study will be stopped immediately.

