**(5) DURATION:**

The study recruitment and intervention will occur during one season. Each participant will participate in at least 2 planned study visits that may take up to 3 hours. Data analysis will continue for a 2 year period following the final enrollment.

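### The protocol is inconsistent on who stops the study for harm, ties one stop to preliminary analyses it never defines, and dates no safety review during the season of collar wear

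*Combined protocol and SAP*

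**What the plan says.** Three statements bear on stopping the whole study for harm.

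- Section (13), Risk/Benefit Analysis: "The safety officer will evaluate all adverse events and will determine if early stopping of the study due to safety concerns is warranted".
- Section (14), Data Safety & Monitoring, on the same officer: "will act in an advisory capacity to the Principal Investigator (PI"). The listed duties include to "make recommendations to the PI concerning continuation, termination or other modifications of the trial".
- Section (14), closing paragraph: "If during the, preliminary analyses the research team identifies strong evidence of harm from the Q-collar device the study will be stopped immediately".

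On timing, section (14) fixes one meeting of the officer and the PI before the trial starts. After that, "Meetings with the safety officer will be determined by the PI", although either of them may call an emergency meeting at any time. On exposure, section (5) states: "The study recruitment and intervention will occur during one season". On outcomes, the Abstract states: "Effectiveness of the device will be determined via differences in longitudinal brain imaging and functional testing following competitive soccer participation". Section (8) plans at least two MRI sessions, one before and one after the season, with extra scans after a diagnosed concussion.

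Other safeguards are written in. Under section (13), an athlete who has an adverse event in the collar is taken out of participation, and adverse events are reported at once. Under section (14), a monitor reviews events as they happen and reports to the PI, and the officer makes periodic assessments that include risk against benefit.

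**The concern.** The participants are healthy athletes aged 14 to 19 wearing a device that compresses the jugular veins. If a safety signal appears and the officer and the PI read it differently, the protocol does not say whose view prevails. Section (13) points to the officer. The duties in section (14) point, by implication, to the PI. The closing clause of section (14) mentions neither, and attaches an immediate stop to analyses that are not a planned step anywhere else.

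The second worry is timing. All collar use falls within one season and no later cohort is planned. A stop that relied on post-season data would leave no collar use to stop.

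The third is that event-by-event review, however prompt, does not by itself set one arm against the other. A modest excess of a common complaint among collar wearers can look unremarkable case by case and show only when events are counted by arm.

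**Working it through.** The protocol gives no stopping boundary, event count or power figure to reproduce, so the check is mainly textual.

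**Step 1: who decides**

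| Place | Who acts | Status of the act |
|---|---|---|
| Section (13) | Safety officer | Determines whether stopping is warranted |
| Section (14), role and duties | Safety officer to PI | Advice and recommendation; decision with the PI by implication |
| Section (14), closing paragraph | Research team | Identifies harm; the study then stops, with no decider named |

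The first two rows give one officer two different standings on the same question. The third adds a route that mentions neither the officer nor a recommendation. The closing part of section (14) also cites Risk/Benefit as section 15, Risks as 14, Privacy as 18 and Confidentiality as 19. In this protocol they are sections 13, 12 and, for the last two together, 15. That suggests the text was not reconciled with the current document.

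**Step 2: what data exist while collars are worn**

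| Data | Available in season? |
|---|---|
| Pre-to-post imaging and functional change | No, apart from tests after a diagnosed concussion |
| Adverse events and diagnosed concussions | Yes |
| Accelerometer impacts, collar-use tracking, monthly questionnaires | Yes |
| Adverse events summarised by arm | Could be compiled, but not planned |

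The reaction-time and oculomotor analyses in section (9) compare groups across the pre- and post-season sessions, so they too need the second visit.

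**Step 3: could the preliminary analyses be concussion counts instead?**

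Inputs: up to 150 athletes (section 6); rates of 4.5 per 10,000 and 0.36 per 1,000 athletic exposures (section 3); two-sided 0.05 (section 9). Assumptions, because the protocol gives no figure: 75 per arm; 30, 60 or 90 exposures per player; a collar rate two or three times the no-collar rate; independent Poisson counts.

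Expected no-collar concussions = 75 × exposures × rate. For example, 75 × 60 × 0.00045 = 2.0.

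Power uses the exact conditional test. Given n concussions in all, the collar count is binomial (n, 0.5) under equal rates, and harm is declared when the upper-tail probability is at most 0.025. Five out of five in the collar arm gives 0.5^5 = 0.031, which is not enough. Six out of six gives 0.5^6 = 0.016. So at least six concussions are needed before the test can reject at all.

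| Rate | Exposures per player | Expected, full season | Power, doubled rate: full / mid-season | Power, tripled rate: full / mid-season |
|---|---|---|---|---|
| 4.5 per 10,000 | 30 | 1.0 | 0.7% / 0.0% | 3.7% / 0.3% |
| 4.5 per 10,000 | 60 | 2.0 | 4.6% / 0.7% | 17.5% / 3.7% |
| 4.5 per 10,000 | 90 | 3.0 | 9.2% / 2.4% | 31.2% / 10.3% |
| 0.36 per 1,000 | 30 | 0.8 | 0.3% / 0.0% | 1.8% / 0.1% |
| 0.36 per 1,000 | 60 | 1.6 | 2.8% / 0.3% | 11.7% / 1.8% |
| 0.36 per 1,000 | 90 | 2.4 | 6.5% / 1.2% | 23.1% / 6.1% |

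At mid-season, power is at most 2.4% for a doubled rate and 10.3% for a tripled one. A formal in-season test of concussion counts would therefore rarely show harm. The protocol gives no expected rate for other collar-related events, so the same sum cannot be done for them.

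**The case against.** The strongest reply is that the statements form one chain: the team sees a signal, the officer judges whether stopping is warranted, the officer recommends, and the PI acts. The PI may also belong to the research team. Much of this stands. A reader might infer three decision-makers who exclude one another, and the text does not support that: the PI decides only by implication, and the closing clause is in the passive and names no decider. What the chain does not settle is a disagreement between officer and PI.

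A second reply is that section (14) never says the preliminary analyses use imaging or functional data, and that other data accrue in season. That also stands. A reader might infer that the written harm stop depends on data arriving after exposure. The documents support only a conditional statement, and the firm complaint is that the analyses are undefined.

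A third reply is that oversight in season is real: individual halting, immediate reporting, evaluation of all adverse events by the officer, event-time review by the monitor, periodic assessments, and emergency meetings that the officer can call without the PI. This stands in full. It would be wrong to infer that athletes are unmonitored during wear, or that only the PI can convene a review. What remains is that the periodic assessments have no dates and no by-arm summary is required.

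Finally, a by-arm table has little power. For concussion that is correct, which is why it should be descriptive and not a test.

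**Conclusion.** The point holds as an inconsistency to reconcile and a cheap improvement to safety review, not as a finding that participants lack protection. Two defects rest on the text alone: the officer's standing on a safety stop differs between sections (13) and (14), and the preliminary analyses that trigger an immediate stop have no stated content, timing or threshold. A third is an omission: the only safety meeting with a fixed time is before the trial, and no by-arm adverse-event summary is planned during wear.

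That an immediate stop could come too late to matter depends on the inference that the preliminary analyses are the pre- and post-season outcomes. The exposure concerned is one season in up to 150 athletes; about 75 with collars assumes an equal split, which the protocol does not state. The concussion figures rest on that split and on 30 to 90 exposures per player. They show only that a formal in-season test would be weak. The point does not bear on the estimate of the device's effect.

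**What to change.** 1. Reconcile sections (13) and (14) into one statement of who decides to stop the study for harm and on what information, including what happens if the officer and the PI disagree. Which role decides, and by what criterion, is for the sponsor and the IRB.
2. In the closing paragraph of section (14), say what the preliminary analyses are, who runs them and when. Keep the harm-stop provision.
3. Give the existing safety officer a short descriptive table of adverse events and collar-wear problems by arm at one or two dated points in the season, in addition to the event-driven review already planned. State that no formal test will be applied. The table need not contain the imaging outcomes, so it need not affect their analysis.
4. Correct the section cross-references in section (14) at the same time.

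Cost: protocol wording, one or two short tables and a little coordinator time, with no new staff. The limitation is that few events are expected, so the table can prompt a closer look but cannot establish or exclude harm.
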